**Secondary**

Establish if there is any discomfort associated with the ultrasonic propulsion treatment.

Qualify and quantify associated complications from the ultrasonic propulsion procedure.

Demonstrate the ability to move stones in a controlled direction.

Demonstrate the ability to move both large stones ( $> 5$  mm) and small stones ( $\leq 5$  mm).

Demonstrate the ability to move an obstructed stone and an associated reduction in pain and/or hydronephrosis.

Demonstrate a reduction in stone volume

Sponsor: \_\_\_\_\_  
[name]

Date: \_\_\_\_\_

Principal Investigator: \_\_\_\_\_  
[name]

Date: \_\_\_\_\_

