Study Treatment – Investigative – All Subjects: The investigational examination is expected to take 30 minutes to 1 hour and will be performed by either a certified sonographer or physician identified as an investigator for this study and previously trained on the device. The study will take place after consultation with at least one urologist and with at least one physician in attendance.

- a) Prior to the ultrasound study, participants will complete a baseline pain questionnaire.
- b) A photo of the subject's skin in the region where the probe will be positioned will be taken.
- c) Participants will undergo a diagnostic ultrasound examination by a certified physician or sonographer with the investigational device. The sonographer and physician will verify the stone is visible on ultrasound and near the location identified on the most recent diagnostic imaging, if available.

- d) Audio and video of the exam will be recorded. Select images of the kidney anatomy and stone will also be captured using the screen capture functionality of the investigational software. A second photograph of the skin in the region where the probe was positioned will be taken between the screening examination and stone pushing.
- e) Participants will undergo stone pushing with the investigational device. The operator will begin with low output and increase the output as necessary. The subject will be directly asked if they experienced any sensations with each of the first three pushes. The subject will be advised to report if they feel any change in sensation with the remainder of the study – they will no longer be asked directly. A maximum of three pushes should be attempted from a single probe position and focus. If the stone does not relocate, the operator should alter the angle of approach by (first) rotating the probe to a new angle of approach, (second) repositioning the probe, and (last) repositioning the subject for a more optimal transducer to stone angle (i.e. so as to not push the stone against the tissue wall.)

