- f) The study staff will monitor the real-time ultrasound image during each burst applied. If echogenicity related to cavitation within the tissue is observed, the treatment will be paused for 1 minute. The treatment will resume at a reduced dose level. This procedure will be repeated as echogenicity related to cavitation in the tissue is continued to be observed. If the treatment setting is reduced to 50 W/cm^2 and cavitation is still observed, the study will be stopped.
- g) Select ultrasound images extending over the duration of the Push and a listing of the system settings, including the target location and Push power, will be recorded automatically to the system hard drive. The output voltage, patient position, stone position, and result of the Push burst will also be recorded manually. There are three potential types of motion for each push pulse, 1) no motion, 2) moved but trapped within a confined space, such as a calyx, 3) translation of the stone to a new location. A fourth option that can be recorded is U) unintended Push. This occurred occasionally with the animal studies through accidental activation of the touch screen.
- h) With Probe 1 (C5-2 transducer) a maximum of 120 Push bursts will be delivered in a single session and a maximum of 40 Pushes will be delivered to a single location. With the SC-X probe, a maximum on-time of 5 minutes will be delivered in a single session. If the operator switches probes, the sum of the percentage of the limits of use for either probe cannot exceed 100% (e.g., 90 pulses with the C5-2 probe is 75% of the total 120, so 25% of the 5 minute total, or 1 minute 15 s total ON time could be used with SC-X.)
- i) Participants will immediately undergo a second diagnostic ultrasound exam to confirm the location of the stone after treatment. Audio and video of the exam will be recorded and select images of the kidney anatomy and stone will also be captured.
- j) A third and final photograph of the skin in the region where the probe was positioned will be taken at the conclusion of the investigational study.
- k) Participants will complete a second questionnaire at the completion of the exam addressing any discomfort or pain they may have felt related to the procedure.

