### **1.3 Study Analysis**

Safety will be determined by the frequency and severity of any adverse events. Effectiveness of the device will be measured by the % of stones moved and average distance of stone motion. The frequency of stone motion in the desired direction (i.e. toward the UPJ or away from the UPJ) will also be assessed. For the observation/medical expulsive therapy population (1a) and stone fragment population (3), the time between treatment and any reported stone passage will be an additional effectiveness parameter. For the obstructing stone population (4), change in pain status and hydronephrosis status, in addition to time between treatment and any reported stone passage, will be additional effectiveness parameters. Sub-categories will include the average number of pushes and the average treatment time.

Safety of ultrasonic propulsion: Safety is a difficult parameter to establish, particularly for the obstructing stone population who are already experiencing symptoms and subjects receiving SWL and URS treatment, since both these procedures may result in potential confounding

complications (see Table 2). In addition, all patients, at any time, could experience complications associated with the natural passage of a stone, such as renal colic, irrespective of having received our investigational treatment.

A method for evaluating complications associated with the investigational study is listed in the bullet points below. Adverse events (AEs) that occur during or after the study will also be subdivided into procedure AEs and device AEs. Procedure AEs are defined as morbidity / mortality events that may occur no matter what device is used. Examples include heart rate changes during treatment, anesthesia issues, discomfort from lying on an exam table, or for this case, intermittent urinary obstruction and other pain events associated with kidney stones. Examples of device AEs include irritation where the probe was in contact with the skin or an AE that occurs as a result of a software issue.

- The number and level of procedural and device AEs identified during and after the investigational procedure will be established.
- The number and severity level of the AEs will be compared with potential occurrences with routine care.
- Medication use will be reported for each subject. The results will be compared against the baseline level of pain medication used by the general stone population that falls within the same treatment group.

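### In same-session subjects the two pain questionnaires enclose both diagnostic scans and all pushes, so their scores alone do not separate propulsion discomfort from scanning discomfort

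*Protocol*

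**What the plan says.** One of the protocol's secondary objectives reads "Establish if there is any discomfort associated with the ultrasonic propulsion treatment". The measurements that serve it are in section 1.2, Study Treatment:

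- Step a: "Prior to the ultrasound study, participants will complete a baseline pain questionnaire".
- Step c: "Participants will undergo a diagnostic ultrasound examination by a certified physician or sonographer with the investigational device".
- Step d: "A second photograph of the skin in the region where the probe was positioned will be taken between the screening examination and stone pushing". No pain rating is placed at this pause.
- Step e: "The subject will be directly asked if they experienced any sensations with each of the first three pushes". After that, "The subject will be advised to report if they feel any change in sensation with the remainder of the study", and direct questioning ends.
- Step i: a second diagnostic scan follows the pushing.
- Step k, which closes the session: "Participants will complete a second questionnaire at the completion of the exam addressing any discomfort or pain they may have felt related to the procedure".

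Three further provisions bear on the point.

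- The pre-treatment text for populations 1-3 calls for a pain questionnaire before and after the screening exam, but only when that exam is at a different time or day from the investigational session. Advance ultrasound screening is itself optional. The corresponding text for population 4 mentions no such pair.
- The source of any discomfort a participant expresses is to be identified and recorded.
- Subjects treated during ureteroscopy complete neither session questionnaire, because they are under anesthesia.

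Section 1.3 divides adverse events into procedure and device events and gives "discomfort from lying on an exam table" as an example of a procedure event.

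**The concern.** The objective concerns discomfort from propulsion, but the questionnaire interval holds several other possible sources: probe pressure during two scans, repositioning of the probe and the subject, and a session expected to last 30 minutes to an hour. Step k also asks about the procedure and does not name the pushes. A higher score at step k than at step a could come from any of these.

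The diagnostic scan uses the same device on the same subject just before pushing, so it is a natural within-person control. The protocol uses it as one for skin, with photographs before the scan, between scan and pushing, and at the end. It applies the same idea to pain through the screening-exam questionnaire pair, but leaves out subjects whose scan and pushing are in one session. A rating that was not taken cannot be recovered by any later analysis plan.

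At stake is how a reported increase is read. It could be charged to the device when the scan caused it, or put down to scanning when the pushes caused it.

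**Working it through.** The protocol states no figure on this point to reproduce. The check is the order of events, followed by a count.

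**Order of events in the session (section 1.2)**

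| Step | Event | Pain questionnaire? | Skin photograph? |
|---|---|---|---|
| a | Baseline questionnaire | Yes | No |
| b | First photograph | No | Yes |
| c | Diagnostic scan | No | No |
| d | Pause between scan and pushing | **No** | Yes |
| e to h | Pushing, repositioning if needed | No (verbal question at pushes 1 to 3) | No |
| i | Second diagnostic scan | No | No |
| j | Third photograph | No | Yes |
| k | Second questionnaire | Yes | No |

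There are two session questionnaires, and neither falls between the scan and the pushing. The change from a to k is the sum of three parts: scan c, the push period, and scan i with the remaining table time. One number cannot identify three parts.

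**What the other provisions add**

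- *Direct questions.* They are specific to the push, but cover three pushes. With Probe 1 the session cap is 120 bursts, so at full use 3 / 120 = 2.5% of bursts are covered. A session with fewer bursts has a larger share covered. Step e starts at low output and allows increases, so later pushes at higher output may fall outside direct questioning.
- *Volunteered reports and recorded source.* These run to the end of the session and do attribute discomfort to a cause. They depend on the subject speaking up and on a judgment made on the spot in an unblinded study, and they give no score.
- *Separate screening pair.* This is a true scan-only contrast, but it is conditional on timing, rests on an optional exam, and is stated for populations 1-3 only.

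**Upper bound on the cases affected (Table 1, treatment cases)**

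- Total: 15 + 18 + 42 + 22 + 5 + 20 = 122.
- Less the URS row, taken to be the cases treated under anesthesia: 122 − 18 = 104.

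The true number is lower by those who have a separate scan pair, which the protocol does not count. The figure is also in cases, not subjects: the footnote to Table 1 says at least 5 subjects were recruited across more than one population. The documents give no rate of discomfort from scanning alone, so the number of cases with an ambiguous score is not estimated.

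**The case against.** The strongest reply is that the protocol does not rest on the questionnaires alone. Subjects are asked about each of the first three pushes, told to report later changes, and have the source of any discomfort recorded. Audio and video of the exam are kept. For a first-in-human feasibility study that wants to know whether there is any discomfort, questioning during the pushes is a reasonable method. Section 1.3 nowhere defines discomfort as the change from step a to step k. The forms are not in the document, and the step k form may ask about scanning and pushing separately.

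Much of this stands. A reader might infer that propulsion discomfort cannot be separated from scan discomfort at all, or that every awake case is affected. The text supports neither: attribution is collected during the session, and some subjects in populations 1-3 may have the scan-only pair. A reader might also infer that a rating before the first push would settle whether an event is a device or a procedure event. It would not, because section 1.3 makes that division by cause and not by time. Stone pain during pushing could be a procedure event, and skin irritation from the scan could be a device event.

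What the reply does not meet is narrower. Even a step k form that asked about scanning and pushing separately would rely on recall at the end of the session. No same-session subject has a score taken after scanning and before pushing, and the safeguards that apply to these subjects either stop at the third push or wait for the subject to speak.

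**Conclusion.** The point holds as a modest weakness in measurement. It is neither a contradiction nor a numerical error. In subjects scanned and treated in one session, the questionnaire scores at steps a and k do not by themselves separate propulsion discomfort from scanning and positioning discomfort. The other safeguards reduce the gap without closing it. For population 4 the scan-only questionnaire pair is not stated at all.

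The size is at most 104 treatment cases. This assumes that Table 1's planned distribution is met (the protocol says it is not binding), that the URS row is the anesthetized group, and that all other rows are awake. The setting of the Dislodging row is not described; any anesthetized cases there would lower the bound. The conclusion does not depend on the count, since it follows from the order of the steps.

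**What to change.** Make two additions to section 1.2, Study Treatment, for awake subjects:

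- In step d: *At the time of the second photograph, after the diagnostic exam and before the first push, the subject completes the pain questionnaire.*
- Before step i: *Directly after the last push and before the second diagnostic exam, the subject gives a brief pain rating on the same scale.*

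The second rating is needed because a change from step d to step k would still contain the step i scan.

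Report the change from a to d as scan discomfort, and from d to the rating after the last push as push-period discomfort. State that the push period still includes any repositioning done during pushing. Use both as supporting information when attributing adverse events, not as the rule that classifies them. Keep step k as the whole-session report.

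The cost is a minute or two of extra questionnaire time per session, mostly at a pause that already exists, with no added procedure or staff. Table 1's footnote indicates that some subjects have already been recruited, so the change can apply only to sessions still to come.

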### 1.1 Study Population

A total of 259 subjects will be recruited for this study. Subjects will be recruited with the aim of obtaining participants from each of the following populations:

- 1a) Subjects with non-obstructing stones managed under observation or with medical expulsive therapy (*De Novo* population),
- 1b) Subjects scheduled for shock wave lithotripsy (SWL) or ureteroscopy (URS) laser lithotripsy, to be treated with the investigational device pre-operatively,
- 2) Subjects scheduled for URS laser lithotripsy, to be treated with the investigational device during the procedure, (URS population)
- 3) Subjects with residual stones at follow-up to lithotripsy treatment, (RCT population) and
- 4) Subjects reporting to the emergency department (ED) or clinic with a symptomatic and/or obstructing stone (Acute population).

Typical stone sizes for population groups 1a and 3 will be  $\leq 5$  mm. Stones for population groups 1b, 2, and 4 will range up to 20 mm.

Subjects will be recruited with the intent to treat 159 individuals, which includes 42 individuals randomized to the control arm of the RCT population. This leaves the potential for 100 screen exclusions. An estimated distribution of subjects across the treatment populations is provided in Table 1. This study is not restricted to the exact numbers listed in this table as more or fewer screen exclusions may be encountered across the different populations. In addition, this protocol does allow subjects to be recruited into multiple arms and receive multiple investigative treatments. Thus, the total number of treatment cases may exceed 117. However, the total number of individual subjects treated will not exceed 117; the total number of controls will not exceed 42; the total number of enrolled subjects will not exceed 259.

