- l) The subject may be provided with a strainer to collect stones during the three week follow-up period. In some investigational procedures passing a stone is unlikely and not relevant to the study so no strainer will necessarily be provided. The subject may also be provided with a medical diary sheet to record their medication use during the three week follow-up period. The diary is a copy of clinical research form 6B.
- m) The subject may be provided with subsidized parking pass for the duration of the research study.
- n) The subject may be provided with bottled water throughout their stay for the research study to help with hydration.

The study will cease immediately if the participant requests that the study end or if the participant experiences significant pain and/or discomfort. If at any point the participant expresses some level of discomfort, the source of the discomfort will be identified, recorded, and resolved if possible. The operator will use the usual safety procedures for operating a clinical diagnostic ultrasound instrument, including using the ALARA principle.

Exceptions for the URS participants receiving treatment during the surgical procedure.

- a) The subject will not complete a baseline pain questionnaire because the investigation procedure will be completed with the subject under anesthesia.
- d) The subject will not be asked if they feel any sensation related to the push as they will be under anesthesia.
- d) The subject will not be moved to any new scanning positions once the URS guide is inserted.
- g) The subject will not be given a post-study pain questionnaire since they will not be awake and accessible for several hours (after recovery). This is not a relevant timeline for obtaining this information; the questionnaire should be delivered immediately following the procedure.

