#### Additions for participants with an obstructing stone

- A urine culture will be ordered for all subjects undergoing treatment to evaluate for the definitive presence of infection in follow-up.

Follow up – Routine Care: As part of the routine treatment patients may be asked to strain their urine and retain stones. Patients may also be prescribed alpha blockers to facilitate stone passage, as well as pain medications to take as needed. Surgical (SWL and URS) participants will also be seen for an ultra-low-dose CT, plainfilm KUB and/or renal ultrasound exam post treatment, as standard care.

Follow up – Investigative –Subjects Undergoing Ultrasonic Propulsion or Enrolled in a Control Group: Research staff will contact the patients each week for three weeks and review their charts each week for the longer of a) 90 days or b) follow-up imaging has been completed to

assess for acute colic events, stone passage, and/or additional interventions/adverse events. Subjects will be asked to record the date of any stone passage since the investigational study. Pain medication taken by the participant will be recorded and converted to Morphine equivalents. With the exception of subjects who underwent the investigational study prior to their surgical treatment, all subjects will be scheduled for follow-up visit if it is not already prescribed as part of their routine care. The subject will be scheduled either for a low dose CT, plainfilm KUB, ultrasound, or a combination of KUB and ultrasound as follow-up. In the case of multiple study treatments, the subject will undergo only 1 follow-up CT; ultrasound and/or plainfilm KUB will be used for any additional follow-up requirements. A certified letter will be sent to any subjects lost to the three week follow-up or post-study imaging visit. The letter will be sent if the subject cannot be reached within four weeks following the study.

In addition, specifically for participants with an acute obstructing stone, subjects will be telephoned with the results of the urine culture test when infection is indicated. This may occur through standard-of-care or by the research team.

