- Short-term complications (within 90 days) identified from follow-up contact and medical chart reviews will be recorded including type and frequency. The results will be compared to the types and frequency of complications expected in stone patients on average.
- The presence and degree of hydronephrosis will be compared between the research study visit and follow-on clinical visit. The result will be compared to stone patients on average.

Effectiveness of ultrasonic propulsion: The pre- and post- ultrasound images, video data, and manual data recorded during each push pulse will be used to evaluate stone motion. The motion associated with each push will be categorized based upon the following criteria: 1) no motion, 2) moved but trapped within a confined space, such as a calyx, 3) translation of the stone to a new location, or U) unintended activation of the Push pulse. The distance achieved for motion #3 and an estimate of the total distance moved for the entire treatment will also be determined. Lastly, the anatomical position of each stone will be identified. From these data, quantitative measurements can be made as to the effectiveness of the clinical device in moving stones. The analysis can be made over all subjects, but also broken down based on group, stone location, or stone size groupings.

- % occurrence of each motion level achieved per total number of pushes
- % occurrence of each motion level achieved as a function of anatomical location.
- Average distance moved for motion levels 3
- Total distance moved per stone

- For subjects enrolled in the long term study, % occurrence of clinical stone events and length of time to those events from the investigative study.

Stone Passage: Stone passage will be identified either from the subject urine screen, chart review, or post-treatment imaging compared to pre-treatment imaging. If the stone was captured and sent for stone analysis, the size and type of stone will also be documented.

- The number of ultrasonically treated stones that passed (spontaneously without additional surgical procedures) will be reported.
- If available, the time between the investigational ultrasonic intervention and stone passage will be recorded.

Metrics for Success: The following metrics will be used as a measure of success for an individual study.

- By any measure, the stone moved more than 2 mm.
- The treatment procedure was tolerable to the patient.

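### The strainer and medication diary are optional and described only within the device session, so noticing and dating of stone passage may differ between the randomised arms of population 3

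*Protocol*

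**What the plan says.** All references are to the Protocol.

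- **Where the tools are issued.** Section 1.2 lists the steps of the study treatment under the label "Study Treatment – Investigative – All Subjects". Step l, near the end, reads "The subject may be provided with a strainer to collect stones during the three week follow-up period" and then "The subject may also be provided with a medical diary sheet to record their medication use during the three week follow-up period". The diary is form 6B. The stated reason for leaving out a strainer is the type of procedure: "In some investigational procedures passing a stone is unlikely and not relevant to the study so no strainer will necessarily be provided".
- **Who the controls are.** Section 1.1 plans to treat 159 individuals, "which includes 42 individuals randomized to the control arm of the RCT population". Table 1 sets 42 RCT treatment cases beside them.
- **What follow-up covers.** The investigative follow-up paragraph of section 1.2 applies to "Subjects Undergoing Ultrasonic Propulsion or Enrolled in a Control Group". It provides weekly contact for three weeks, weekly chart review for at least 90 days, compulsory recording of pain medication and an imaging visit. It also says "Subjects will be asked to record the date of any stone passage since the investigational study". It names neither a strainer nor a diary.
- **How passage is established.** Section 1.3: "Stone passage will be identified either from the subject urine screen, chart review, or post-treatment imaging compared to pre-treatment imaging". The same section makes the interval from treatment to reported passage an effectiveness parameter for populations 1a and 3.
- **Routine care.** Section 1.2 says that patients may be asked to strain their urine. This is optional and is not tied to arm.

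**The concern.** Population 3 is the only randomised part of an unblinded study. Its passage outcome depends on a subject noticing a small fragment and giving it a date. If treated subjects leave their session with a strainer and controls do not, the arms differ in how well passage is observed as well as in how often it happens. Better capture in the treated arm would produce more reported passages and more exact dates there, which favours the device.

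Two features of the text make this more than a missing detail. First, the reason given for withholding a strainer cannot apply to population 3, where passage is an effectiveness parameter, yet the option is not lifted for that population. Second, passage dates are collected with the investigational study as the reference point. A control has no device treatment, and the text names no other start date for controls.

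**Working it through.** The protocol gives no figure for this point, so there is none to reproduce. The check has two parts: what the text secures for each arm, and how large an error could be under stated assumptions.

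**1. Does step l reach the controls?**

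- The label over the list refers to all subjects, but step e has participants undergo stone pushing without condition. Read to include controls, the list would treat them.
- The preceding paragraphs are labelled for populations 1-3 and for population 4, so the label most naturally means all populations.
- Section 1.1 caps treated subjects (117) and controls (42) separately: 117 + 42 = 159.
- Where controls are meant, the follow-up paragraph says so.

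The text therefore does not provide the tools to controls. It also does not say that they are denied them, because no control visit is described.

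**2. What is common to both arms?**

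| Source | Treated | Control | Gives a date? |
|---|---|---|---|
| Study strainer (step l) | optional | not stated | yes, if used |
| Routine-care straining | optional | optional | yes, if used |
| Weekly contact, 3 weeks | yes | yes | only if passage was noticed |
| Chart review | yes | yes | only if an event was charted |
| Follow-up imaging | yes | yes | no; it shows only that the stone has gone by then |
| Pain medication record | required | required | not applicable |

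Whether a stone passed has a common backstop in imaging. The date does not.

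**3. Illustration of size.** Inputs: 42 per arm (section 1.1 and Table 1). True passage p is the same in both arms. Detection d is the proportion of passages recorded. Both p and d are assumptions; the protocol gives neither.

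Spurious difference = p × (d treated − d control).

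- p = 40%, d = 90% v 60%: 0.40 × 0.90 = 36%; 0.40 × 0.60 = 24%; difference 12 points, or 42 × 0.12 = 5.0 subjects.
- p = 40%, d = 80% v 70%: 32% v 28%; difference 4 points.

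The table gives the spurious difference and, in brackets, the probability that a two-sided 5% Fisher exact test rejects although true passage is equal:

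| Detection, treated v control | p = 20% | p = 40% | p = 60% |
|---|---|---|---|
| 100% v 100% | 0 (2.9%) | 0 (3.4%) | 0 (3.4%) |
| 95% v 85% | 2 points (3.3%) | 4 points (4.4%) | 6 points (6.6%) |
| 95% v 75% | 4 points (4.7%) | 8 points (8.4%) | 12 points (16.4%) |
| 90% v 60% | 6 points (7.5%) | 12 points (16.4%) | 18 points (33.5%) |

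**4. Effect of imaging as a second source.** Assume that imaging independently detects 80% of passages. Combined detection = 1 − (1 − d) × (1 − 0.80).

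- Treated: 1 − 0.10 × 0.20 = 98%.
- Control: 1 − 0.40 × 0.20 = 92%.
- Spurious difference at p = 40%: 0.40 × 0.06 = 2.4 points, down from 12.

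This recovers only whether a stone passed. A passage found by imaging alone still has no date.

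**The case against.** A reader might infer that controls never attend a session, that passage and medication are therefore recorded more completely in treated subjects, and that nothing can be repaired afterwards. The documents do not support this.

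- **Attendance and provision.** No control visit is described, so non-attendance is an inference. Step l is optional, so treated subjects may lack a strainer too. The stated reason for omitting one is procedure type, not arm.
- **Completeness.** One follow-up rule covers both arms, including the request for passage dates and the imaging visit. No actual gap in recording is shown.
- **Medication.** Recording is compulsory in both arms and the diary is only an aid. Section 1.3 compares medication with use in the general stone population, not with the control arm. The medication side is minor.
- **Repair.** Comparison of imaging before and after can largely recover whether a stone passed. The three sources in section 1.3 are alternatives with no ranking.

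It can also be said that section 1.3 counts passage of ultrasonically treated stones and measures time from treatment, so no passage contrast between arms is set out. The outcome stated for the long-term study, clinical stone events, does not depend on strainers. This is fair, and it limits the weight of the point. It does not remove it: population 3 is the randomised population, time to reported passage is listed for it, and controls are asked for passage dates under the common rule.

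What stands is narrower. Equal provision is not secured, and the common sources do not replace a strainer for dating small fragments. Unblinded self-report would remain even with equal tools.

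**Conclusion.** The point holds as a risk of unequal ascertainment that is cheap to prevent, not as a demonstrated bias. The protocol ties optional strainers and diaries to the device session and does not provide them to the randomised controls. Noticing of passage may differ by arm, and dating more so. The diary adds little.

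The size is unknown. In the illustrations the false difference in recorded passage runs from 2 to 18 points when imaging is ignored. For one of those cases, 40% true passage with 90% v 60% detection, it falls from 12 to 2.4 points when independent imaging detection of 80% is assumed. All passage and detection rates are assumptions, and the error matters only if the gap in detection is large. Exact passage dates are the most exposed quantity, because no source shared by both arms reliably supplies them.

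This is a matter of trial conduct that the protocol itself sets. A later analysis plan cannot recover a date that nobody observed.

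**What to change.** For population 3, amend section 1.2 so that:

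1. every subject in both arms receives the strainer, form 6B and the same straining instructions at one defined index visit, for example randomisation, and staff discretion in step l is removed for this population;
2. the same scripted passage and medication questions are asked at each of the three weekly contacts in both arms;
3. time to passage is counted from that index date in both arms, in place of the present reference to the investigational study.

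The cost is about 42 extra strainers and diary sheets, a short protocol change and a slight burden on controls. If the device session falls on a later day than the index visit, the treated arm's clock will include some time before treatment, so the session date should be recorded as well. No treatment changes.
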